Vascular leak is a fundamental feature of CAs, mediating hemorrhage and the associated accumulation of non-heme iron (including hemosiderin). Pre-clinical studies demonstrated rescue of vascular permeability and decreased lesional iron deposition with ROCK inhibitors and statins³¹, and B-cell depletion therapy³² in murine CA models recapitulating the human disease. [name]'s group in Chicago implemented a novel MRI application of assessing iron deposition in human CAs using quantitative susceptibility mapping (QSM)³³⁻³⁶. Mean lesional QSM was shown to reflect actual iron concentrations assessed by mass spectroscopy in resected human CA specimens³⁵. Researchers in Chicago and New Mexico optimized a second technique, dynamic contrast enhanced quantitative perfusion (DCEQP) measure on MRI in human subjects, reflecting mechanistically postulated vascular hyper-permeability^{33, 34, 37-39}. The [name] team used both QSM and DCEQP successfully in over 200 CA subjects and showed strong inter-observer agreement in QSM and DCEQP measurements, stability of both measurements in clinically stable lesions, and reproducibility across MRI instrument platforms at the Chicago site^{36, 38}. As predicted by the conservation of mass hypothesis, CA lesions with greater permeability (K_i) had higher lesional iron content (QSM)³⁶, and lesional iron content was greater in older patients and in CAs with prior SH³⁶. More recent studies demonstrated a significant increase of mean lesional QSM and DCEQP K_i in human CA lesions manifesting interval SH or growth during longitudinal follow-up, while these did not change in stable lesions³³. There were tight, sensitive and specific thresholds of QSM and DCEQP increases in association with clinical events³³. Therefore, it is postulated that the QSM and DCEQP may be used as *in vivo* measures of hemorrhagic activity and vascular leak, respectively, and may reflect sensitive, clinically meaningful therapeutic effect in human CAs. No other biomarkers have been as linked mechanistically to CA, nor associated as closely with clinical events.

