Specific Aim 3. Time to recurrent SH will be analyzed using Kaplan Meier method and Cox proportional hazards regression approach. Rates of recurrent SH/patient/year from initial SH qualifying event, and SH/patient/year from enrollment (potentially more relevant for trial modeling) will be estimated along with 95% CIs. Changes in mean lesional QSM and K_i during 1 and 2-year epochs will be compared using paired t-test or Wilcoxon signed rank test to assess changes within patients over time, including 95% CIs. To test predictive, monitoring or surrogate outcome hypotheses, two sample t-test or Wilcoxon rank sum test will be used to compare such changes between patients with and without recurrent SH. Categorical variables such as proportions of patients with a drop in mRS score ≥ 1 point, difference in EQ-5D and PROMIS 29 scores, NIHSS scores, between patients with and without recurrent SH will be compared using Chi-square or Fisher's exact test. Associations of baseline characteristics (sex, lesion locations, familial/sporadic) and recurrent SH as a binary outcome (yes/no) will be assessed using

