univariable and multivariable logistic regression and reported as odds ratios and 95% CIs. Depending on the number of recurrent SH over the 2-year period, we may analyze re-bleeds as a continuous outcome and the associations of baseline features or biomarkers assessed using linear regression. Performance of final model(s) will be assessed using r^2 in the case of linear regression, area under the curve (AUC) and Hosmer Lemeshow goodness of-fit test⁵⁵ in the case of logistic regression, or concordance index in the case of Cox proportional hazards regression. AUCs between various models (univariable) will be compared using the method proposed by DeLong et al⁵⁶. For biomarkers, we will create a binary variable (yes/no) depending on whether the % change in mean lesional QSM or K_i during 1-year epochs exceed previously defined respective thresholds (+ 5.8% QSM and +39.6% for K_i)³³ that were significantly associated with new clinical events at high sensitivity and specificity in previously stable lesions. We will then assess the association of this newly created variable (“biomarker event”) with SH rate treated as continuous (using two sample t-test or Wilcoxon rank sum test) and binary (using Chi-square or Fisher’s exact test) outcomes of interest. Finally, we shall compare the sensitivity/specificity of changes in mRS, QOL, and NIHSS scores, and lesional QSM and K_i in relation to SH during the same epochs, using McNemar’s test with SH (yes/no binary) as the reference standard. All tests will be 2-sided and p-values <0.05 considered statistically significant.

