9.3 POPULATIONS FOR ANALYSES

Cavernous angiomas with symptomatic hemorrhage (CASH) are most likely to re-bleed and cause further neurologic sequelae. It would be desirable to develop a drug that stabilizes CASH, and prevent recurrent bleeding. CASH with recent bleed, where surgical resection is not undertaken, are the most likely cases to be followed expectantly per current evidence based guidelines, with clinical equipoise for testing novel therapies to prevent re-bleeding. They are the most likely cases to be targeted for clinical trials.

Appropriate and complete statistical modeling of data collected by the sites for both SCA/FUBV arms are imperative to the planning, development, and completion of a successful Phase III interventional trial. The most critical component is the accurate assessment of the enrollment rates of CASH across several sites, as well as the between-site variability in these estimates. Both within and between sites variability will be used to adequately power a Phase III trial, will be calculated by developing random-effect models along with using appropriate link functions quantifying the rates of CASH in these models.

As a follow-up step, in-depth data analyses will be performed using the demographic, imaging, clinical and biomarker data collected. These are applied to develop models assessing how predictive each of these factors is to the development of recurrent SH. Understanding which factors are most predictive of SH will be crucial in developing a covariate adaptive randomization scheme for the Phase III trial that insures proper balance in these prognostic factors between treatment arms. Finally, statistical assessments of changes in lesional iron content and permeability biomarkers, QOL, mRS, and NIHSS during follow-up of CASH patients will be performed. Understanding how these measures change over time will be an important step in the process of developing hypotheses on the effect of treatment on these as putative secondary or surrogate outcomes, or as potential composite outcomes.

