Predictors of SH: Two sample t-test or Wilcoxon rank sum test will be used to compare such changes between patients with and without recurrent SH. Categorical variables such as proportions of patients with a drop in mRS score ≥ 1 point, between patients with and without recurrent SH will be compared using Chi-square or Fisher's exact test. Associations of baseline characteristics (sex, lesion locations, familial/sporadic) and recurrent SH as a binary outcome (yes/no) will be assessed using univariable and multivariable logistic regression and reported as odds ratios and 95% CIs. Depending on the number of recurrent SH over the 2-year period, we may analyze re-bleeds as a continuous outcome and the associations of baseline features or biomarkers assessed using linear regression. Performance of final model(s) will be assessed using r^2 in the case of linear regression, area under the curve (AUC) and Hosmer Lemeshow goodness of-fit test⁵⁵ in the case of logistic regression, or concordance index in the case of Cox proportional hazards regression. AUCs between various models (univariable) will be compared using the method proposed by DeLong et al⁵⁶. For biomarkers, we will create a binary variable (yes/no) depending on whether the % change in mean lesional QSM or K_i during 1-year epochs exceed previously defined respective thresholds (+ 5.8% QSM and +39.6% for K_i) that were significantly associated with new clinical events at high sensitivity and specificity in previously stable lesions³³. We will then assess the association of this newly created variable ("biomarker event") with SH rate treated as both continuous (using two sample t-test or Wilcoxon rank sum test) and binary (using Chi-square or Fisher's exact test) outcomes of interest. Finally, we shall compare the sensitivity/specificity of changes in mRS, QOL, and NIHSS scores, and lesional QSM and K_i in relation to SH during the same epochs, using McNemar's test with SH (yes/no binary) as the reference standard. All tests will be two-sided and p-values <0.05 considered statistically significant.

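### The contrast of QSM and K_i change by recurrent bleeding is assigned to predictive as well as monitoring or surrogate hypotheses, but nothing requires the change to be measured before the bleed

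*Combined protocol and SAP*

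**What the plan says.** Section 9.1 (Specific Aim 3) first describes within-patient changes in mean lesional QSM and K_i over 1- and 2-year epochs. It then says: "To test predictive, monitoring or surrogate outcome hypotheses, two sample t-test or Wilcoxon rank sum test will be used to compare such changes" between those with and without recurrent SH. One test therefore serves three kinds of hypothesis. Section 9.4.1 gives the same test as the opening of a paragraph on predictors: "Predictors of SH: Two sample t-test or Wilcoxon rank sum test will be used to compare such changes".

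Other text bears on prediction without setting a time order:

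- Section 9.3 promises "models assessing how predictive each of these factors is to the development of recurrent SH", with biomarkers among the factors, and adds: "Understanding which factors are most predictive of SH will be crucial in developing a covariate adaptive randomization scheme for the Phase III trial".
- Section 9.1 offers an option: "we may analyze re-bleeds as a continuous outcome and the associations of baseline features or biomarkers assessed using linear regression". It does not say whether the biomarker is a baseline value or a change.
- Section 9.1 lists "concordance index in the case of Cox proportional hazards regression" among the performance measures, so a Cox model is planned. Its covariates are not named.
- The logistic model in 9.1 and 9.4.1 gives sex, lesion location and familial or sporadic disease as its baseline characteristics.
- The only explicit timing link between biomarker change and SH is concurrent. The McNemar comparison concerns "lesional QSM and K_i in relation to SH during the same epochs".

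On the data, section 9.2 places research scans at baseline, year 1 and year 2. Sections 4.3 and 7.1 keep patients who re-bleed without excision in the study for their remaining scheduled assessments. On biology, section 4.2 reports a "significant increase of mean lesional QSM and DCEQP K_i in human CA lesions manifesting interval SH or growth during longitudinal follow-up", and no change in stable lesions.

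**The concern.** A predictor must be known before the event that it predicts. Here an SH before the year-1 scan falls inside the baseline-to-year-1 change, and every SH before the year-2 scan falls inside the 2-year change. Given the background evidence in section 4.2, a larger change in re-bleeders may simply be the trace of the bleed. That is what a monitoring or surrogate marker should show, and it says nothing about whether the marker foretells a bleed.

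The distinction matters because the plan names prediction as a purpose in its own right: in the Aim 2 statement in section 3, in the contrast itself in 9.1, and in the modelling goals in 9.3. Followed as written, the test can report a consequence of bleeding as a predictor of it.

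**Working it through.** **Inputs (section 9.2 unless stated).** 120 enrolled; 30% lost or missing; SH rate 10-20% per year; 80% power; alpha 0.05, two-sided (9.1).

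**1. The plan's own figure.** Evaluable patients: 120 × 0.70 = 84, or 168 patient-years over two years. Expected SHs: 168 × 0.10 = 16.8 and 168 × 0.20 = 33.6, the plan's 17 and 34. A two-sample t-test (noncentral t) with 17 v 67 and 34 v 50 patients has a detectable difference of 0.77 and 0.63 SD. This reproduces the stated 0.63-0.77 SD.

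**2. When first bleeds fall relative to the year-1 scan.** Assume a constant rate r and N = 84.

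| Quantity | Formula | r = 0.10 | r = 0.20 |
|---|---|---|---|
| First SH before month 12 | 84(1 − e^−r) | 8.0 | 15.2 |
| SH-free at month 12 | 84e^−r | 76.0 | 68.8 |
| First SH in months 12-24 | 84(e^−r − e^−2r) | 7.2 | 12.5 |
| Any SH in 2 years | 84(1 − e^−2r) | 15.2 | 27.7 |
| No SH in 2 years | 84e^−2r | 68.8 | 56.3 |

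So about half of the re-bleeders (8.0 of 15.2; 15.2 of 27.7) bleed before the year-1 scan. Only about 7-12 patients can have a change measured before their first recurrent SH.

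**3. What the contrast returns for a marker that predicts nothing.** Simulation with 20,000 runs per setting: exponential SH times; change drawn from N(0,1), plus d SD if the bleed precedes the scan; pooled t-test. Every re-bleeder is assumed to have a later scan. The value of d is an assumption. Entries are the proportion of runs with p<0.05.

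| Contrast | r = 0.10, d = 0.5 | r = 0.10, d = 1.0 | r = 0.20, d = 0.5 | r = 0.20, d = 1.0 |
|---|---|---|---|---|
| 2-year change v any SH | 0.41 | 0.92 | 0.57 | 0.99 |
| Year-1 change v any SH in 2 years | 0.15 | 0.44 | 0.21 | 0.60 |
| Year-1 change v later SH, patients SH-free at the scan | 0.05 | 0.05 | 0.05 | 0.05 |

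**4. What properly ordered tests can detect (80% power).**

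- Baseline marker against any later SH, groups 15.2 v 68.8 and 27.7 v 56.3: 0.80 and 0.66 SD.
- Year-1 change against later SH, groups 7.2 v 68.8 and 12.5 v 56.3: 1.11 and 0.89 SD. Power at the plan's own 0.77 and 0.63 SD is 49% and 51%.

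**The case against.** **The text is incomplete rather than wrong.** It does not forbid comparing year-1 change with later SH, the contrast suits two of its three named uses, and section 10.1.4 has the statisticians refine the plans during year 1. This is fair. Even so, the current text gives the predictive hypothesis to this test and sets no order anywhere.

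**Prediction is covered elsewhere.** Section 9.3 plans predictive models, and baseline marker values precede follow-up SH by construction. This stands in part: much of the remedy is naming covariates in models already foreseen. But the regression on biomarkers is optional and does not specify baseline values.

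**The simulated percentages are partly circular.** With d set at the plan's detectable difference (0.77 SD at 10% per year, 0.63 SD at 20%), the 2-year contrast is significant in about 75% of runs. That is essentially the planned monitoring power under another name. This stands. It is why the size is given only as an illustration over an assumed range. Two further limits apply: patients whose lesion is resected leave follow-up and may have no post-bleed scan, and the constant rate is an assumption, since section 9.4.1 treats homogeneity across years as a question to be assessed.

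**A stronger reading to avoid.** From section 9.3 a reader might infer that a spurious change result would pass straight into the Phase III randomization scheme. The documents do not support this. A change over one or two years of follow-up would not normally be known at randomization. The subgroups pre-defined to inform stratification or adaptive randomization (9.1, 9.4.2) are sex, genotype and lesion location.

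**Conclusion.** The point holds for the predictive use only. A contrast whose change interval contains the bleed cannot show that the change foretells the bleed, and no other section supplies an ordering rule. That conclusion needs no simulation. It follows from the scan schedule, the retention of re-bleeders and the evidence in section 4.2.

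The size is uncertain. For an assumed post-bleed rise of 0.5-1.0 SD, a non-predictive marker is called significant in about 41-99% of runs (2-year change) or 15-60% (year-1 change against any SH), against a nominal 5%. These figures rest on 84 evaluable patients, 10-20% per year, a constant hazard and a later scan for every re-bleeder.

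A reader might also infer that the monitoring analysis, the power statement or the choice of certifiable outcomes in section 10.1.2 is undermined. None is: the same-interval comparison is appropriate for monitoring and surrogate use, and 0.63-0.77 SD reproduces. The change should be made, but it is a limited one.

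**What to change.** 1. In sections 9.1 and 9.4.1, label every change-versus-SH contrast that shares an interval as monitoring or surrogate only, and move these contrasts out of the Predictors of SH paragraph.
2. State that any predictive claim uses markers measured before the SH. Name baseline QSM and K_i as covariates in the planned Cox model for time to recurrent SH. Time since the qualifying SH can be an optional sensitivity adjustment. It need not be required: section 4.2 reports higher iron in lesions with prior SH, but no gradient with time since SH.
3. Add, as exploratory only, a landmark analysis: change from baseline to the first follow-up scan against SH after the actual date of that scan, among patients SH-free and under follow-up on that date. Using the scan date rather than month 12 copes with the ±1 month window (1.2), rescheduled visits (7.2) and the option of 6- and 18-month visits (10.1.2).

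The cost is a few sentences in the plan and modest programming, with no added visits or scans. The Cox analysis already needs SH dates, and time from SH is among the listed variables (9.4.1). The downside is low information in the landmark analysis: about 7-12 events, a detectable difference of about 0.89-1.11 SD, and about 50% power at the plan's own effect sizes. A null landmark result should therefore not be read as evidence against prediction.

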8 STUDY ASSESSMENTS AND PROCEDURES

All eligible subjects will be identified by the study team at each site. Based on clinic schedules and current patient databases, all CCM patients with a symptomatic hemorrhage within the last 12 months (of screening) are eligible for the trial. Sites will screen neurology, neurosurgery, and neurointerventional radiology clinic schedules, MRI schedules, and attend Neurovascular rounds to help identify potential subjects. Additionally, study sites will rely on referrals from the various services listed above, or self-referrals via web searches and through the Angioma Alliance, a patient support group. Once identified, the study coordinator at each site, along with the site PI, will screen the subject for basic eligibility. Screened subjects not scheduled to come in for a clinical visit within their eligibility window will be contacted by the study coordinator or PI to explain the study and determine if the subject is interested. When the subject comes in, either for a standard clinic visit or for a study visit, the study team will review the subject's medical history to ensure the subject meets the inclusion criteria. The trial will be explained and informed consent obtained. After consent is obtained a physical exam (height, weight, vital signs) will be completed, a baseline modified Rankin Score obtained, and EQ-5D, PROMIS 29, and NIH stroke scale assessments completed. The study team will also collect information about the subject's history, pertinent to the disease (history of seizure, resection of other lesions, etc.). All subjects at the FUBV sites (enrolled to the FUBV arm) will have a MRI scan including the additional sequences for research as specified in Specific Aim 2 (QSM/DCEQP). All women of childbearing age will undergo a urine or serum beta-HCG pregnancy test prior to MRI to confirm no pregnancy, per local institutional guidelines.

Subjects enrolled in the FUBV arm will return for 2 follow up visits: one at 12 months and the other at 24 months. Excluding the informed consent process, all baseline procedures will be repeated. Subjects will have completed their participation upon completion of the baseline visit procedures (SCA arm) or the year 2 visit (FUBV arm). All subjects enrolled in the SCA arm will have one study visit only.

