9.4 STATISTICAL ANALYSES

9.4.1 GENERAL APPROACH

Data collection. Key variables to be collected in this study will be decided on by all stakeholders in Year 1. At a minimum, these will include patient demographics, genotype, baseline MRI lesion features of the hemorrhagic CA (size, location), time from SH, prior bleeds/dates, and diagnosis date. Functional status will be measured using the modified Rankin Scale (mRS) score⁵⁷, Euro-QoL⁵³, PROMIS29⁵², and NIH Stroke Scale. PROMIS 29 short forms are an assessment of anxiety, depression, and fatigue, and have been validated for use in several common neurological disorders. Presence of obstructive sleep apnea. Recent findings suggest that sleep apnea results in decreased blood flow to the brain. This transient ischemia may be implicated in CA hemorrhage. Sleep apnea questions will be included in the dataset and response analyses as described under the topic Predictors of SH.

Data harmonization. Common data elements from each site will be reviewed, updated, and harmonized using an iterative, stepwise process based on DataSHaPER (DataSchema and Harmonization Platform for Epidemiologic Research) recommendations⁵⁸⁻⁶⁰. Questionnaires, codebooks, and protocols, etc. at the 3 established CA databases (Table 2) will be compiled and distributed for review. A series of Executive Committee teleconference calls will be held in Year 1 to decide on a set of 'target' data elements for potential clinical trials, as has been similarly done with the consensus process for developing clinical guidelines paper¹⁷. The EDHC and DCC will then develop standardized electronic data entry forms and codebooks for data collection. Each site shall be trained in abstracting and entering data for their cases online. Data will be collected prospectively in Years 2-5. Analysis datasets will be generated quarterly by the DCC for quality control analysis by EDHC.

Event Rate: Time to recurrent SH will be analyzed using Kaplan Meier method and Cox proportional hazards regression approach. Rates of recurrent SH/patient/year from initial SH qualifying event, and SH/patient/year from enrollment (potentially more relevant for trial modeling) will be estimated along with 95% CIs.

Biomarker changes over 2 years: Changes in mRS, EQ-5D, PROMIS 29, and NIHSS scores, mean lesional QSM and K_i during 1 and 2-year epochs will be compared using paired t-test or Wilcoxon signed rank test to assess changes within patients over time, including 95% CIs.

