We will calculate the proportion and exact 95% confidence interval (CI) of CASH cases among all CA cases at each SCA site and overall. Baseline characteristics will be summarized using chi-square tests for categorical variables and t-tests for continuous variables. Baseline Euro-QoL and PROMIS29 measures will be validated for use in CAs. Euro-QoL and PROMIS29 measures are scored on the T-score metric, with a mean of 50 and standard deviation (SD) of 10 in a referent population (mild, moderate, and severe impairment is defined as 0.5-1.0 SD, 1.0-2.0 SD, or 2.0+ worse than the mean, respectively). Spearman correlation coefficients will be calculated between mRS and Euro-QoL and PROMIS29 scales, and mean scores of Euro-QoL and PROMIS29 will be stratified by mRS levels. This analysis will allow us to determine ceiling effects of scores and how well the Euro-QoL and PROMIS29 data are distributed in CASH cases.

Homogeneity of event rates, biomarker changes, and other endpoints in years 1 and 2. This will be assessed, as it impacts (1) sample size calculations for time averaged assessments of the impact therapies, and (2) whether future trials should be conducted for 1 or 2 years.

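### Section 9.1 sends EQ-5D, PROMIS 29 and NIHSS score differences to chi-square or Fisher with no cut-point, while section 9.4.1 compares changes in the same scores by t-test or Wilcoxon

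*Combined protocol and SAP*

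**What the plan says.** Section 9.1 (Specific Aim 3) opens its list with "Categorical variables such as proportions of patients with a drop in mRS score" of at least one point and continues: "difference in EQ-5D and PROMIS 29 scores, NIHSS scores, between patients with and without recurrent SH will be compared using Chi-square" or Fisher's exact test. The mRS drop is the only item in that list with a defined category. Elsewhere in the Aim 3 text of 9.1, the t-test and Wilcoxon sentences concern the imaging biomarkers: "Changes in mean lesional QSM and K_i during 1 and 2-year epochs will be compared using paired t-test or Wilcoxon signed rank test". The two-sample test that follows refers back to those biomarker changes.

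Section 9.4.1 covers the same ground with a different allocation. Its paragraph on changes over two years reads: "Changes in mRS, EQ-5D, PROMIS 29, and NIHSS scores, mean lesional QSM and K_i during 1 and 2-year epochs will be compared using" a paired t-test or signed rank test. The next paragraph adds: "Two sample t-test or Wilcoxon rank sum test will be used to compare such changes between patients with and without recurrent SH". The chi-square sentence in 9.4.1 is otherwise close to the one in 9.1, but it names only the mRS drop.

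On scale, 9.4.1 states: "Euro-QoL and PROMIS29 measures are scored on the T-score metric, with a mean of 50 and standard deviation (SD) of 10". Section 9.1 says the same of EQ-5D. NIHSS is called a score without further description. Section 8 has all these instruments collected at enrolment ("a baseline modified Rankin Score obtained, and EQ-5D, PROMIS 29, and NIH stroke scale assessments completed") and repeated at 12 and 24 months in the FUBV arm. The synopsis (1.1) defines the secondary endpoint as change in functional status and quality of life in years 1 and 2 relative to baseline.

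**The concern.** One comparison, patients with against patients without recurrent SH on three instruments, has two families of test. The 9.1 version cannot be run as written, because chi-square needs categories and none is defined for these scores. The mild, moderate and severe bands in 9.1 and 9.4.1 classify a score against a referent population. They do not define a change, and none is given for NIHSS. An analyst following 9.1 would have to choose cut-points, possibly after seeing the data.

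The effect of a bleed on functional status is a secondary objective. The milestone table in 10.1.2 also has the study decide between SH alone and QOL or biomarkers as certifiable outcomes. With only 17-34 re-bleeds expected, the comparison has little power to spare.

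**Working it through.** **Inputs from section 9.2.** 120 cases, 30% allowance for dropout or missing data, two years of follow-up, 10%-20% re-bleed rate per year, 80% power, alpha 0.05. Section 9.1 makes all tests two-sided.

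**Step 1. Group sizes.** 120 × 0.70 = 84 evaluable. 84 × 2 = 168 patient-years. 168 × 0.10 = 16.8 and 168 × 0.20 = 33.6, which the plan rounds to 17-34 SHs. Taking one SH per patient, the groups are 17 v 67 and 34 v 50.

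**Step 2. Reproduce the plan's figure.** By the normal approximation, detectable d = (1.960 + 0.842) × √(1/n1 + 1/n2):

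- 17 v 67: 2.802 × 0.2716 = 0.761
- 34 v 50: 2.802 × 0.2223 = 0.623

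The noncentral t gives 0.770 and 0.630, which match the stated 0.77 and 0.63 SD. So the sample-size section rests on an unadjusted two-sample t-test of a continuous variable. That is the 9.4.1 analysis, not the 9.1 one.

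**Step 3. Illustrative cost of cutting (cut-points assumed).** For a normal score, a median split has relative efficiency 2/π = 0.637, so the detectable difference is divided by √0.637 = 0.798:

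- 0.63 / 0.798 = 0.79 SD
- 0.77 / 0.798 = 0.97 SD

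Equivalently, power at the plan's own detectable difference becomes about Φ(2.802 × 0.798 − 1.960) = Φ(0.276) = 61%.

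Exact enumeration at 0.77 SD (17 v 67) and 0.63 SD (34 v 50) agrees:

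| Assumed cut | Groups | Chi-square power | Fisher power |
|---|---|---|---|
| no-SH median | 17 v 67 | 57% | 47% |
| midpoint of the two means | 17 v 67 | 63% | 55% |
| 1 SD above no-SH mean | 17 v 67 | 61% | 54% |
| no-SH median | 34 v 50 | 59% | 56% |
| midpoint of the two means | 34 v 50 | 61% | 59% |
| 1 SD above no-SH mean | 34 v 50 | 57% | 50% |

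**Step 4. Cross-check against the plan's categorical figure.** Section 9.2 gives 32-40% as the detectable difference for categorical outcomes, the larger value belonging to 17 SHs. Cut at the midpoint, a 0.77 SD shift is 65.0% v 35.0%, a gap of 30.0 points against the 40 needed. A 0.63 SD shift is 62.4% v 37.6%, a gap of 24.8 points against 32. On the plan's own figures, a shift detectable on the continuous scale falls short once it is cut. The base rate behind 32-40% is not stated, so this is a consistency check only.

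**Step 5. Baseline adjustment, for the optional sensitivity analysis.** With baseline/follow-up correlation ρ, equal SDs and similar baselines, the ANCOVA to change-score variance ratio is (1 + ρ)/2, and the detectable difference scales by its square root. The documents give no ρ. For assumed values of 0.3, 0.5, 0.7 and 0.8 the multiplier is 0.806, 0.866, 0.922 and 0.949, a reduction of about 19%, 13%, 8% and 5%.

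**The case against.** **9.1 may mean proportions with a change on each instrument.** On this reading it adds a categorical analysis and does not replace the continuous one. The plan already treats mRS both ways in 9.4.1, and the McNemar comparison in both sections needs yes/no changes in QOL and NIHSS. This is a fair reading, and 9.1 does not say that chi-square is run on raw scores. But 9.1 still contains no continuous between-group test for these scores and no threshold. The power loss in steps 3 and 4 arises only if 9.1 is followed in place of 9.4.1.

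**A reader might infer that omitting the baseline score as a covariate is an error, and that ANCOVA should be required.** The documents do not support that:

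- The synopsis defines the endpoint as change from baseline, so a change score matches it, and 9.4.1 already uses baseline by subtraction. Section 9.1 does not say whether its difference is a change from baseline.
- Recurrent SH is a non-randomised grouping formed after baseline. ANCOVA and change scores then differ by (1 − ρ) times the baseline difference. For an assumed imbalance of 0.3 SD and ρ = 0.5, that is 0.5 × 0.3 = 0.15 SD. Neither is automatically the less biased.
- The precision gain in step 5 assumes similar baselines and a ρ that the plan does not give.
- The plan first examines ceiling effects and score distributions, so requiring ordinary ANCOVA now would be premature.

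**The setting is modest.** This is a secondary endpoint in an observational study, and 10.1.4 foresees statisticians refining the plans in year 1. That limits the severity but does not resolve the conflict.

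**Conclusion.** The conflict between 9.1 and 9.4.1 is real, and the 9.1 allocation is wrong as written for scores that the plan treats as T-scores (EQ-5D and PROMIS 29). For NIHSS the documents state no scale, but 9.1 gives no category for it either. The 9.4.1 analysis agrees with the scale, the endpoint definition and the basis of the sample size.

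The size is illustrative. Under a median split the detectable difference would rise from 0.63-0.77 to about 0.79-0.97 SD. Under the assumed cut-points, power at the plan's own effect sizes would fall from 80% to about 57-63% (chi-square) or 47-59% (Fisher). These figures assume normal scores and one SH per patient. Patients stay in follow-up after an SH, so repeat events could make the re-bleed group smaller than 17-34.

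A reader might also infer that the sample size is wrong. It is not: 0.63-0.77 SD reproduces for the analysis in 9.4.1. The absence of a baseline covariate is a matter of choice and not an error.

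**What to change.** 1. In 9.1, delete the EQ-5D, PROMIS 29 and NIHSS score differences from the chi-square sentence.
2. In 9.1, as in 9.4.1, compare changes from baseline in these scores between patients with and without recurrent SH by two-sample t-test or Wilcoxon rank sum, with 95% CIs.
3. Keep chi-square or Fisher for the proportion with an mRS drop of at least one point.
4. Optionally, prespecify a baseline-adjusted model (ANCOVA, or rank ANCOVA) as a sensitivity analysis. State that with non-randomised SH groups it can estimate a different quantity from the change score, and that any precision gain depends on the baseline/follow-up correlation and on similar baselines.
5. Deleting the scores from the chi-square list does not settle the McNemar comparison, which still needs a stated threshold for QOL and NIHSS changes. Any threshold should be fixed before the data are examined.

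The cost is a wording change in the statistical section. No new data, visits or sample size are needed.
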